7.3 Vital Signs

Vital sign data (blood pressure [BP], pulse, and weight) will be summarized by treatment, and listed by subject and sequence.

Change from baseline will also be summarized by treatment group using data from Periods II and IV. The incidence of PCS values will be presented, with a focus on new-onset PCS values.

PCS ranges for these parameters are provided in Table 4.

Table 4: List of Potentially Clinically Significant Ranges for Vital Sign Parameters

Systolic blood pressure:
Low: < 90 and decrease ≥ 30 mm Hg
High: >140

Diastolic blood pressure:
Low: < 50 and decrease ≥ 20 mm Hg
High: >90 and increase ≥ 20 mm Hg
Pulse
Low: <50 bpm and Decrease ≥ 30 bpm
High: >100 and Increase ≥ 30 bpm
Weight
$\geq 10\%$ increase from baseline
$\geq 10\%$ decrease from baseline

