14. Significant tremor which would interfere with recording balance and walking.
15. Uncorrected vision disturbance or vestibular problems that would affect gait and balance.
16. Symptomatic hypotension or symptomatic orthostatic hypotension (e.g. subjective feeling of lightheadedness, faintness, dizziness, or fear of collapsing due to these symptoms, reported by the patient and/or caregiver on clinical history).
17. Symptomatic bradycardia which in the opinion of the investigator may place the subject at risk of syncope.
18. History of frequent and/or unexplained syncopal episodes.

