### **8.3.2.3. Vital Signs**

Height will be measured at the screening visit only. Body weight will be measured at each visit. Vital signs will be measured after the subject has been in the supine position for 5 minutes and will include temperature, systolic blood pressure, diastolic blood pressure, heart rate, respiratory rate, and temperature. For subjects who are unable to lie down, the vital signs can be measured after the subject has been in the seated position for 5 minutes.

Postural changes in systolic blood pressure, diastolic blood pressure, and heart rate will be measured again approximately 3 minutes after standing.

Abnormal vital signs that are clinically significant according to the investigator or designee should be recorded as Medical History (if found during Visit 1) or an AE (if found during any visit after Visit 1).

The equipment used (scale, blood pressure monitor, etc.) should remain consistent across the study for a given subject.

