7.4 ECGs

ECG data will be listed by sequence, subject, and time point. Change from baseline will be summarized by treatment group using data collected during the double-blind treatment periods plus 7 days.

The ECG analysis will include a careful review of QTcF values. As part of this review, a summary of the number (percent) of subjects with QTcF values in the following ranges will be provided: ≤ 450 msec, >450 to ≤ 480 msec, >480 to ≤ 500 msec, and >500 msec. This will be performed at ANY time during the double-blind treatment periods plus 7 days (where the highest QTcF value will be used for that assessment) and presented by treatment group.

The overall Investigator interpretation of ECG by treatment (shifts from baseline) will be tabulated. The incidence of PCS values will be presented, with a focus on new-onset PCS values in Table 5.

Table 5: List of Potentially Clinically Significant Ranges for ECG Parameters

QTcF Interval:
High: ≥ 500 msec only
High: Increase ≥ 60 msec only
High: ≥ 500 and Increase ≥ 60

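### SAP 7.3: the joint low-pulse rule flags very few slow pulses, and the SAP text defines no analysis of the postural blood pressure and heart rate taken at every clinic visit

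*SAP*

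**What the plan says.** SAP 7.3 presents the incidence of PCS values, with emphasis on new-onset ones, using Table 4:

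- Low pulse: "Low: <50 bpm and Decrease ≥ 30 bpm". High pulse: "High: >100 and Increase ≥ 30 bpm".
- Low systolic: "Low: < 90 and decrease ≥ 30 mm Hg". The low diastolic row has the same form, with limits of 50 and 20 mm Hg.
- High diastolic: "High: >90 and increase ≥ 20 mm Hg". High systolic is the exception: a level above 140 with no change condition.

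On summaries, the section says: "Vital sign data (blood pressure [BP], pulse, and weight) will be summarized by treatment, and listed by subject and sequence". Change from baseline is also summarised by treatment. SAP 4.1.2 sets baseline at the pre-dose assessment of Visit 3 (Period II) or Visit 5 (Period IV).

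Protocol 8.3.2.3 takes a resting reading supine, or seated if the subject cannot lie down, and then: "Postural changes in systolic blood pressure, diastolic blood pressure, and heart rate will be measured again approximately 3 minutes after standing". Footnote 7 to the schedule of events asks for this at every visit, in both the protocol and the SAP.

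SAP 7.4, Table 5, treats QTcF differently. It has one row for level alone, one for change alone ("High: Increase ≥ 60 msec only") and one for both together.

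**The concern.** A PCS table exists to count individual outliers that a mean change can hide. If its limits are almost unreachable, an empty row says little.

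This matters more here than in many trials. Inclusion criterion 3 requires a previous fall. Exclusion 16 removes only symptomatic hypotension and symptomatic orthostatic hypotension, and exclusion 17 removes "Symptomatic bradycardia which in the opinion of the investigator may place the subject at risk of syncope". Subjects with an asymptomatic postural drop or slow pulse can therefore be enrolled. Safety and tolerability is the only secondary objective, and vital signs are one of its endpoints. The trial collects the data needed to compare postural change between treatments, but the SAP text does not say how they will be compared.

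**Working it through.** **Inputs.** The limits come from Table 4. The pulse and blood-pressure rows do not say what the decrease is measured from; I read it as baseline under SAP 4.1.2. Readings are taken as whole numbers. The documents give no operating characteristics for Table 4, so there is no figure to reproduce.

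**1. Low pulse (no assumed distributions).** A reading is flagged if it is at or below min(49, baseline − 30).

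| Baseline (bpm) | Flagged at or below (bpm) |
|---|---|
| 60 | 60 − 30 = 30 |
| 65 | 65 − 30 = 35 |
| 70 | 70 − 30 = 40 |
| 75 | 75 − 30 = 45 |
| 79 or more | 49 |

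The 50 bpm limit governs only when baseline − 30 ≥ 49, that is, from a baseline of 79. A fall from 60 to 35 is a decrease of 25 and is not flagged.

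**2. Low blood pressure (same form).** Systolic: min(89, baseline − 30). A reading of 89 counts only from a baseline of 119 or more, and a baseline of 110 must reach 80 or less. Diastolic: min(49, baseline − 20). A reading of 49 counts only from a baseline of 69 or more.

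**3. Postural change.** Table 4 compares a reading with one taken two weeks earlier; a postural drop compares two positions at one visit. The first cannot stand in for the second. Even if the decrease were read as postural, a standing fall from 140 to 105 (35 mm Hg) would fail, because 105 is not below 90.

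**4. Size for pulse (illustrative).** Assumptions, none from the documents: normal pulse with mean 65, 70 or 75 bpm, total SD 10 and within-subject SD 6 or 8; one on-treatment reading per period; 40 subjects (top of the planned 30–40); 1,000,000 simulated subjects per setting.

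| Mean shift (bpm) | New readings below 50, per 40 | Flagged by Table 4, per 40 | Chance of at least one flag in 40 |
|---|---|---|---|
| 0 | 0.17–1.96 | 0.002–0.10 | 0.2%–9.5% |
| −5 | 0.7–5.0 | 0.02–0.41 | 2%–34% |
| −10 | 2.3–10.3 | 0.14–1.3 | 13%–74% |
| −15 | 5.7–17.4 | 0.76–3.45 | 54%–97% |

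At a shift of −10 bpm the joint rule catches 3% to 24% of new readings below 50.

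**5. High systolic (illustrative).** Assumptions: mean 125 to 140 mm Hg, total SD 15, within-subject SD 7 or 10, no drug effect. Then 6% to 16% of subjects per period (2.5 to 6.2 of 40) newly exceed 140, and 60.5% to 86.7% of those rose by less than 20 mm Hg. Level-only counts are easier to interpret with a change-only count beside them.

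**The case against.** The PCS table is one output among several. SAP 7.3 summarises change from baseline in blood pressure and pulse by treatment, where a mean shift would appear whatever the flag rule. SAP 7.4 summarises ECG change and tabulates shifts in the investigator's interpretation, and Protocol 8.3.2.4 specifies an ECG machine that calculates heart rate. Under Protocol 8.3.2.3, vital signs judged clinically significant after Visit 1 become adverse events, and SAP 7.1 tabulates treatment-emergent events. SAP 7 lists all safety data, which is readable in full with 30–40 subjects. All of this stands. A reader might infer that pulse or postural signals would be missed; the documents do not support that.

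A reader might also infer that the postural data will never be analysed. That cannot be shown. SAP 1 places the planned tables in a separate spreadsheet not supplied here, and the schedule footnote puts postural readings under vital signs, so standing values may be included. The supportable statement is that the SAP text defines no postural variable, summary or limit.

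A third inference, that these are known risks of the drug, also fails. Exclusions 16–18 are eligibility rules, and nothing supplied says that RVT-101 slows the pulse or lowers standing pressure.

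Finally, one might want a change condition added to the high-systolic row. That would create the same joint form that makes the pulse row insensitive. Chance flags there arise under both treatments, and the comparison is descriptive.

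The remaining routes still leave a gap. Means can hide outliers, listings are not a treatment comparison, and adverse-event capture depends on investigator judgement. None of them specifies a by-treatment postural summary.

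**Conclusion.** The point holds as a gap in specification and sensitivity. The low-pulse rule is very insensitive for ordinary baselines, the low blood-pressure rules share its form, and the SAP text specifies no postural analysis of data collected at every clinic visit. The PCS tables are therefore poorly suited to pulse and postural signals in this population, while other outputs keep some ability to show them.

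The threshold arithmetic is firm once the decrease is read as change from baseline. The simulated ranges rest on assumed means and SDs and show order of magnitude only. A large shift (−15 bpm) would produce at least one flag more often than not in every setting tried. The gap affects reporting of the sole secondary objective, not the primary gait-speed result. It should be corrected because the correction is cheap.

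**What to change.** Amend SAP 7.3 before unblinding:

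- **(a) Three-way reporting.** Present pulse and blood-pressure PCS incidence as level-only, change-only and both, following Table 5. The same rows would show how many systolic readings above 140 involve little change, so that row needs no separate condition.
- **(b) Position and postural summaries.** State which position feeds Table 4. Define the standing-minus-supine change in systolic pressure, diastolic pressure and heart rate, including how a seated resting reading is handled. Summarise it by treatment at Visits 3 to 6, with the incidence beyond a cut-off that the sponsor chooses and fixes in advance. No cut-off is proposed here.

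No new data are needed. The cost is SAP wording, a few table rows and more flagged values to review. Under the pulse assumptions above, level-only reporting would add up to about 2 flagged subjects per 40 in a period with no drug effect (0.17–1.96, against 0.002–0.10 under the joint rule).

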7.4 ECGs

ECG data will be listed by sequence, subject, and time point. Change from baseline will be summarized by treatment group using data collected during the double-blind treatment periods plus 7 days.

The ECG analysis will include a careful review of QTcF values. As part of this review, a summary of the number (percent) of subjects with QTcF values in the following ranges will be provided: ≤ 450 msec, >450 to ≤ 480 msec, >480 to ≤ 500 msec, and >500 msec. This will be performed at ANY time during the double-blind treatment periods plus 7 days (where the highest QTcF value will be used for that assessment) and presented by treatment group.

The overall Investigator interpretation of ECG by treatment (shifts from baseline) will be tabulated. The incidence of PCS values will be presented, with a focus on new-onset PCS values in Table 5.

Table 5: List of Potentially Clinically Significant Ranges for ECG Parameters

QTcF Interval:
High: ≥ 500 msec only
High: Increase ≥ 60 msec only
High: ≥ 500 and Increase ≥ 60

7.5 Physical Examination

Physical examination data will be summarized by treatment group and listed by sequence, subject, and time point.

7.6 Suicidality

The following outcomes are C-SSRS categories and have binary responses (yes/no). The categories have been re-ordered from the actual scale to facilitate the definitions of the composite and comparative endpoints, and to enable clarity in the presentation of the results.

- Category 1 – Wish to be Dead
- Category 2 – Non-specific Active Suicidal Thoughts
- Category 3 – Active Suicidal Ideation with Any Methods (Not Plan) without Intent to Act
- Category 4 – Active Suicidal Ideation with Some Intent to Act, without Specific Plan
- Category 5 – Active Suicidal Ideation with Specific Plan and Intent
- Category 6 – Preparatory Acts or Behavior
- Category 7 – Aborted Attempt
- Category 8 – Interrupted Attempt
- Category 9 – Actual Attempt (non-fatal)
- Category 10 – Completed Suicide
- Self-injurious behavior without suicidal intent is also a C-SSRS outcome (although not suicide-related) and has a binary response (yes/no)

Endpoints based on the above categories are defined below.

- Suicidal ideation: A “yes” answer at any time during treatment to any one of the five suicidal ideation questions (Categories 1-5) on the C-SSRS
- Suicidal behavior: A “yes” answer at any time during treatment to any one of the five suicidal behavior questions (Categories 6-10) on the C-SSRS
- Suicidal ideation or behavior: A “yes” answer at any time during treatment to any one of the ten suicidal ideation and behavior questions (Categories 1-10) on the C-SSRS
- Self-injurious behavior without suicidal intent: a binary response (yes/no)

The number and percentage of subjects with any occurring suicidal events (ideation or behavior) will be presented by treatment group and time point.

A listing of all C-SSRS data will be provided, while a listing of subjects who demonstrated a worsening on any one of the four endpoints will also be provided for pre-and post-treatment (V3 vs V4 and V5 vs V6) including the Day on Treatment the C-SSRS was collected.

7.7 Pregnancy

If any female subjects or female partners of male subjects become pregnant during the study, a listing will be provided.

8 INTERIM AND FINAL ANALYSES

No unblinded interim efficacy or safety analyses are planned for this study. This final analysis will be performed upon completion of the following items:

- The database has been locked according to the Study Data Management Plan
- The list of subjects excluded from Per-Protocol Population has been identified

9 CHANGES FROM THE PROTOCOL TO THIS SAP

There are no meaningful changes from the protocol to this SAP. Additional details and specifications have been included in this SAP to allow for better understanding of the intended procedures.

